- a. Study design, including the sequence and timing of study procedures (distinguish research procedures from those that are part of routine care).

The study will be a randomized controlled trial of RP patients randomized to receive perioperative pharmacologic prophylaxis (subcutaneous heparin; 5,000 units given before surgery and every 8 hours after surgery until discharge) with IPCs or routine care with IPCs alone. No other standard post-RP practices will be affected. Per routine, all patients will be encouraged to ambulate early.

Routine care includes an initial clinic consultation, a preoperative evaluation center (PEC) visit prior to surgery (often done the day before surgery), and a planned 1 to 2 night inpatient stay after surgery. Patients currently receive IPCs but no pharmacologic prophylaxis in our default practice at Johns Hopkins. Patients are often given the option of returning to the Johns Hopkins clinic or local follow-up (with a provider or at home) for urinary catheter removal at around 10 days from surgery. Patients who were referred by outside urologists or providers may then decide if they wish to be followed at Johns Hopkins or locally for routine post-RP surveillance for cancer recurrence. Our current default practice at Johns Hopkins of no pharmacologic prophylaxis is considered inappropriate for most other major surgeries. However, both arms of this trial are considered routine standards of practice in the United States.

Informed consent will be obtained before surgery at either their urology or PEC clinical visit, or in the preoperative area the day of surgery. Eligibility will be confirmed at the time of consent. Patients will be randomized after consent is obtained and their surgery is officially scheduled to minimize dropout. Randomization will be done in blocks and stratified by whether patients choose to undergo an option 30-

day lower extremity Duplex ultrasound (outlined below) and whether they are having open or minimally-invasive (robotic/laparoscopic) surgery.

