Patients randomized to the pharmacologic VTE prophylaxis arm will receive a dose of subcutaneous heparin 5,000 units within 2 hours prior to incision, and subcutaneous heparin 5,000 units every 8 hours after surgery until discharge. Total number of doses received and missed doses will be recorded. No post-discharge pharmacologic prophylaxis will be prescribed. Per routine care, patients will be requested to inform their urologist's office if they experience any symptoms of DVT or PE, or any other concerns, during the first 30 days after surgery. All patients will receive a phone call around 30 days after surgery to assess primary outcomes including documentation of whether they experienced a postoperative VTE episode and any treatment initiated for confirmed VTE. Any patient endorsing symptoms concerning for VTE up to 30 days after surgery will be recommended to undergo urgent evaluation and care, locally or at Johns Hopkins, with imaging/evaluation results forwarded to Johns Hopkins. Patients and their insurance will be responsible for the costs as part of routine care. The 30-day phone call will be the only planned, study-initiated contact after surgery with the patient to evaluate symptomatic outcomes and will be the same for both the control and pharmacologic prophylaxis arms.

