Urologists will initially be blinded to patient randomization and the administration of the preoperative subcutaneous heparin dose to prevent bias on recorded estimated blood loss during the surgery. Postoperatively, administration of subcutaneous heparin will be unblinded during the patient's inpatient stay. Control patients will receive IPCs only and no placebo doses will be administered during their hospital stay. Data analysis will be blinded as to treatment group. Performance and interpretation of lower extremity Duplex screening ultrasound will be blinded to patient randomization. Surveillance bias will be assessed by differential performance of postoperative imaging as described above.

- d. Justification of why participants will not receive routine care or will have current therapy stopped.

All patients will receive routine care. Both arms include patients receiving accepted standards of care.

- e. Justification for inclusion of a placebo or non-treatment group.

The control group in this trial is the group receiving current routine practice at Johns Hopkins with IPCs. The experimental group is the group receiving pharmacologic VTE prophylaxis as practiced at other centers and recommended by most VTE guidelines for major surgery.

- f. Definition of treatment failure or participant removal criteria.

Participants will be removed from the trial if surgery is canceled or not completed for any reason. All patients assigned to the experimental and control arms completing surgery will be included in the study regardless of compliance with pharmacologic prophylaxis doses in an intention-to-treat (ITT) analysis. Patients experiencing an adverse event will be provided appropriate care. Additional per-protocol analyses will be conducted to compare outcomes by compliance with assigned regimen. Patients diagnosed with VTE events will be recommended to obtain routine care locally or at Johns Hopkins per patient preference.

- g. Description of what happens to participants receiving therapy when study ends or if a participant's participation in the study ends prematurely.

Perioperative pharmacologic prophylaxis is only given during the patient's inpatient stay. As mentioned above, all patients will be included in an ITT analysis as possible if they undergo surgery. No planned outcomes will be tracked after the 30-day post-surgical outcomes unless the patient initiates contact.

5. Inclusion/Exclusion Criteria

Inclusion:

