The primary efficacy outcome will be the incidence of symptomatic VTE within 30 days after surgery. A symptomatic VTE event will be defined as any imaging-confirmed VTE diagnosed after evaluation for VTE prompted by the presence of signs/symptoms concerning for VTE. The primary analysis will compare this rate between treatment arms at the 30-day follow-up for all patients. Symptomatic VTE will also include any deaths attributed to a clinically suspected VTE event without imaging confirmation (if autopsy is performed, VTE must be confirmed at autopsy; if autopsy is not performed, clinical suspicion of VTE as the cause will suffice). Symptoms prompting evaluation include:

1. Persistent unilateral or bilateral lower extremity edema
2. Persistent calf pain or cramping
3. Persistent or new chest pain
4. Persistent or new shortness of breath that started suddenly or worsens with exertion
5. Productive cough with bloody sputum
6. Fever and/or tachycardia without any known source of infection
7. Any other clinical concern for DVT or PE

The primary safety outcomes will include three separate measures of incidence of symptomatic lymphocele, incidence of symptomatic hematoma, or major bleeding within 30 days after surgery. Symptomatic lymphocele and symptomatic hematoma will include imaging confirmed events based on imaging pursued at the discretion of the primary attending urologist per routine practice (current routine practice involves imaging only if clinical symptoms suggest possibility of a lymphocele or hematoma). Events will be recorded regardless of the need for intervention (e.g. drain placement by interventional radiology). While screening studies show rates of 25-50% for postoperative lymphocele regardless of surgical approach (open or robotic), the rate of symptomatic lymphocele is thought to be around 10% or less [31,32]. Major bleeding will be defined as the need for transfusion of ≥ 2 units of packed red blood cells after the completion of surgery for anemia attributed to postoperative bleeding or need to return to the operating room for active bleeding.

c. Secondary outcome variables.

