Two planned interim analyses of the primary endpoint will be conducted, after one-third and two-thirds of patients have undergone RP. Early stopping for efficacy or futility will be assessed at these time points. Details are provided below under Interim Analyses.

Statistical analyses: The treatment and control groups will be compared to identify any imbalance after randomization in relevant characteristics. Comparisons will include factors such as age, race, BMI, comorbidities, prostate volume, tumor stage, operative time, and blood loss. Discrete factors will be compared with chi-squared test, and continuous factors will be compared with t-test or Wilcoxon ranksum test if data do not conform to a Gaussian distribution. Analysis of the primary outcome (symptomatic VTE) will compare 30 day post-RP rates between the treatment and control groups, using chi-squared test. Logistic regression will be used if adjustment is required for any potential confounders not balanced by randomization, with the treatment effect estimated by the odds ratio and 95% confidence interval. Similar comparison of univariate rates, and adjusted odds ratios will be used for the 3 primary safety endpoints (lymphocele, hematoma, occurrence of major bleeding), and for the secondary outcome of any VTE (restricted to patients who undergo the 30 day lower extremity Duplex ultrasound). Secondary endpoints with a continuous metric (blood loss, surgical drain output, number of imaging tests (surveillance bias)) will be compared in univariate fashion using t-test or Wilcoxon ranksum, and adjusted analyses will use linear regression. Note that analysis of drain output is confined to patients with drains placed, so it is not protected by the randomization, potentially limiting interpretability if the number of patients is small and confounding factors are not well balanced. All analyses of primary and secondary outcomes will be based on intention to treat (ITT). Per protocol analyses will also be conducted, but treatment success will be based on ITT.

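### Section 4f removes randomized patients whose operation is not completed, possibly after the pre-incision heparin dose, and Section 4g describes a different analysis set

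*Combined protocol and SAP*

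**What the plan says.** All references are to the combined protocol and SAP.

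- **Section 4f, removal:** "Participants will be removed from the trial if surgery is canceled or not completed for any reason".
- **Section 4f, analysis set:** "All patients assigned to the experimental and control arms completing surgery will be included in the study", whatever their compliance with heparin. The plan calls this intention to treat.
- **Section 4g, analysis set:** "all patients will be included in an ITT analysis as possible if they undergo surgery". The sentence opens by referring back to what was said before, so it does not clearly override 4f.
- **Section 4a, randomization:** "Patients will be randomized after consent is obtained and their surgery is officially scheduled to minimize dropout".
- **Section 4a, first dose:** patients in the heparin arm "will receive a dose of subcutaneous heparin 5,000 units within 2 hours prior to incision". Section 6a gives a 3-hour window for the same dose.
- **Section 4c, blinding:** "Urologists will initially be blinded to patient randomization and the administration of the preoperative subcutaneous heparin dose".
- **Section 7b, safety outcomes:** "three separate measures of incidence of symptomatic lymphocele, incidence of symptomatic hematoma, or major bleeding within 30 days after surgery".
- **Section 7d:** every primary and secondary analysis is by intention to treat, but the set is not defined there.

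No section defines a safety population of treated patients or a tabulation of those removed.

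**The concern.** Completing the operation is something that happens after randomization and, in the heparin arm, usually after the first dose. Bleeding can stop an operation, and bleeding is the harm that this trial sets out to measure. A rule that drops every uncompleted operation, whatever the reason, can therefore select patients on an effect of treatment. That is not intention to treat, whatever the set is called.

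The safety comparison is what is at stake. If preoperative heparin leads to some abandoned operations, the removed patients come disproportionately from the heparin arm and are among those most likely to bleed further. Their estimated blood loss and later events would be missing, and heparin would look safer than it is. Sections 4f and 4g also leave open who belongs in the primary analysis.

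**Working it through.** **1. The plan's own figure.** Inputs from Section 7d: 5% versus 1.5%, 333 per arm, one-sided alpha 0.05. The fixed-sample formula is

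power = Φ{[Δ√n − z_α √(2p̄q̄)] / √(p₁q₁ + p₂q₂)}

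with Δ = 0.035, p̄ = 0.0325, √(2p̄q̄) = 0.2508, √(p₁q₁ + p₂q₂) = 0.2496 and √333 = 18.248. This gives Φ[(0.6387 − 1.645 × 0.2508)/0.2496] = Φ(0.906) = 0.818. A group-sequential simulation with looks at 222, 444 and 666 gives 0.824. The stated 82% is reproduced, so the point concerns the text and not the sample size arithmetic.

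**2. Effect on efficacy power.** At the cumulative alpha of 0.048 (Section 7e), power is 0.812 with 333 per arm. If removed patients are not replaced, an assumed 0.3% loss (332 per arm) gives 0.811 and a 2% loss (326 per arm) gives 0.805. The effect is negligible.

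**3. Who is in the analysis set, reading 4f and 4g side by side.**

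| Randomized patient | Can have had heparin? | 4f | 4g |
|---|---|---|---|
| Canceled before the dosing window | No | Out | Out |
| Canceled after the dose, before incision | Yes | Out | Out |
| Opened, then abandoned | Yes | Out | In, on a plain reading |
| Completed | Yes | In | In |

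The third row is where the sections disagree and where a drug effect can drive removal. In the second row both sections drop a patient who may be exposed.

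**4. What removal can lose.** Section 7b defines major bleeding as transfusion of at least 2 units of packed red cells once surgery is complete, or a return to the operating room for active bleeding. Removal can therefore lose a later transfusion, a return to the operating room, a symptomatic hematoma, a VTE within 30 days, and the estimated blood loss (Section 7c). For an operation that ends uncompleted, the starting point of the transfusion criterion is undefined.

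**5. How many patients.** The documents give no non-completion rate. Assuming 0.5% to 2%: 0.005 × 333 = 1.7 and 0.02 × 333 = 6.7, or about 2 to 7 per arm for all reasons together.

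**6. Sensitivity of a safety comparison.** The counts are assumed: 17 of 333 heparin patients with bleeding versus 7 of 333 controls. Each removed heparin patient is assumed to have been an event, and no control patient is removed. The test is the uncorrected chi-squared test.

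| Heparin patients removed | Heparin rate | Difference from 7/333 = 2.10% | p |
|---|---|---|---|
| 0 | 17/333 = 5.11% | 3.00 points | 0.038 |
| 1 | 16/332 = 4.82% | 2.72 | 0.055 |
| 2 | 15/331 = 4.53% | 2.43 | 0.080 |
| 3 | 14/330 = 4.24% | 2.14 | 0.116 |
| 5 | 12/328 = 3.66% | 1.56 | 0.231 |

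With 10 versus 5 events, removing 5 takes the difference from 1.50 points to 0.02. This is the least favorable pattern, not a forecast.

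**7. Interim safety halt.** Section 7e halts the trial for review when the lower 95% confidence bound for major bleeding reaches 5%. With exact or Wilson bounds this needs 11 events in 111 patients, 18 to 19 in 222, or 32 to 33 in 444. At the first look, read by arm, one event is 1/111 = 0.9 points. One or two lost events matter only when the count is already near that boundary.

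**The case against.** The strongest reply is that the harm is smaller than the removal rule suggests. Four parts of it deserve weight.

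- **Endpoint definition.** A reader might infer that 4f deletes the most severe intraoperative bleeds from the primary safety outcomes. The documents do not support that. Under Section 7b an intraoperative bleed, or a death on the table from bleeding, is not in itself a primary safety event; the intraoperative measure is estimated blood loss, a secondary outcome. This stands. What can be lost is blood loss and later events. No mechanism is evident for lymphocele.
- **Follow-up.** A reader might infer that removed patients get no 30-day call. That does not follow either: Section 4a promises the call to all patients, and Section 8c routes unanticipated problems to the investigator and the IRB. The text is ambiguous, which calls for clarification.
- **Blinding.** The urologist does not know the arm during the operation. This limits abandonment driven by knowledge of allocation. It does not limit abandonment caused by heparin.
- **Magnitude.** Every count of removed patients or bleeding events is assumed. It would also be wrong to set a shift in the observed rate against the 5% limit as though that were a ceiling on the point estimate; the rule acts on a lower confidence bound.

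It can also be said that 4g merely restates 4f loosely. If so, the exclusion of uncompleted operations is confirmed and the problem remains.

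**Conclusion.** The point holds in limited form. As written, 4f is a post-randomization and possibly post-exposure exclusion that can depend on a drug effect, and 4g does not resolve it. If heparin causes some operations to be abandoned, the direction is toward no harm. The size is unknown: abandonment may be rare, and the 2 to 7 patients per arm rest on an assumed 0.5% to 2% for all causes together. The illustrated change from p = 0.038 to 0.055 further assumes that the one removed patient was a heparin-arm event. Efficacy power is essentially unaffected, and N stays at 666. The case for acting is that the safety outcomes may involve few events, that data not collected cannot be recovered, and that the correction is cheap.

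**What to change.** 1. Amend 4f and 4g to one analysis set. Exclude only patients whose operation is canceled before a fixed time point defined identically in both arms, regardless of whether heparin was given. A condition based on heparin receipt should not be used, because only one arm can fail it.
2. Keep every other randomized patient, including any whose operation is abandoned, in the intention-to-treat, safety and interim analyses, and state that each gets the 30-day call.
3. Reword the transfusion part of the major bleeding definition in Section 7b so that it also applies after an operation that ends without completion. Without this, a retained patient could still be impossible to classify.
4. List canceled and abandoned cases by arm, with reasons.
5. Reconcile the pre-incision dosing windows in Section 4a (2 hours) and Section 6a (3 hours), so that the time point in item 1 can be defined.

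The cost is a wording amendment, a few extra calls, and slight dilution of the VTE comparison by patients without a completed prostatectomy.

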Early reports of VTEs after prostatectomy noted variable rates from 20% to 50% using screening studies that implemented 125 I-fibrinogen scanning, which has since been outdated due to questionable specificity [9-11]. During the era of Walsh's anatomical approach to the RRP, one series reported a clinical post-operative PE incidence of 2.7% [12-14]. More recent studies attempting to estimate postoperative VTE rates have been flawed by lack of consistent or planned follow-up to specifically monitor symptoms of VTE. Modern rates are thought to have significantly decreased, about 3 to 8-fold in the past 20 years, due to shorter hospital stays, early ambulation, and the advent of robotic and laparoscopic techniques [15]. Current estimates of symptomatic VTE range from 0.2% to 8% with a recent series implementing both mechanical and pharmacologic prophylaxis reporting a rate of 1-2% with several-fold greater risk for undergoing concurrent lymphadenectomy or open surgical approach [15,16]. Generally, the best available evidence is largely derived from series where all patients receive pharmacologic prophylaxis with an overall rate of about 2% [16-19].

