One retrospective study of laparoscopic RP at high-volume centers with no planned follow-up for VTE reported 27 imaging confirmed DVTs and 9 imaging confirmed PEs in 31/5951 (0.5%) patients where over two-thirds received some degree of heparin prophylaxis [20]. The thoroughness of follow-up and events captured across centers, unfortunately, appeared unreliable. For example, one surgeon who utilized preoperative and postoperative heparin prophylaxis reported an overall VTE rate of 6.2% (4.9% DVT, 1.2% PE) while all other surgeons reported rates of <1%. An administrative series from the National Surgical Quality Improvement Program captured a PE rate of 32/8381 (0.4%) after laparoscopic RP, which suggests many more patients would have had symptomatic DVTs making the overall VTE rate several-fold greater [21]. Very few screening studies have been performed in this setting. One study from Indiana performed screening ultrasonography within 1 week of surgery to identify a DVT in 2/245 patients, but an additional 7 patients (3.7% overall) with initially negative ultrasonography presented symptomatically within 2 weeks after surgery, 2 of whom developed PEs [22]. A Chinese screening study detected DVTs in 18/109 (16.9%) patients on postoperative day 3 after RALRP, although only 1 patient had an above the knee DVT requiring anticoagulation [23].

However, controversy remains as to whether pharmacologic prophylaxis significantly contributes to reduced rates of VTE for patients undergoing RP in the modern era of RRP and RALRP. In addition, some urologists have been wary due to an early report, based on 38 patients, of increased rate of lymphoceles associated with subcutaneous heparin after RRP with pelvic lymphadenectomy [24]. Notably, a report from almost 20 years later analyzing 579 patients receiving pelvic lymphadenectomy (533 had concurrent RRP) showed no statistically significant difference in lymphocele rate by screening pelvic ultrasound [25]. No randomized controlled trial has been performed to assess reduction in rates of VTE due to pharmacologic prophylaxis or potential increase in complications such as bleeding and lymphocele.

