Randomization by blocks will be used, with stratification for type of surgery (robotic/laparoscopic vs. open) and subcohort membership (agrees to 30 day ultrasound/does not agree to 30 day ultrasound). Currently at Johns Hopkins approximately 40% of RPs are performed open, with the remainder robotic or laparoscopic, and the subcohort is planned to include 200 patients. Note that patients are randomized within each of the 4 subgroups formed by cross classification of these 2 strata, not randomized to the strata. Therefore, anticipated sizes of the 4 strata are

1. open RP/subcohort member, n=80
2. open RP/not subcohort member, n=186
3. robotic RP/subcohort member, n=120
4. robotic RP/not subcohort member, n=280

Because the above numbers are subject to variability in the choice of surgical approach, randomization lists will increase the number in each of the surgical categories by 20%, i.e. 320 and 480 random assignments will be generated for open and robotic surgeries, respectively. An undisclosed block size will be used to prevent any ability to predict next treatment assignment. The randomization lists will be generated by [name] using SAS PROC PLAN. Although this uses a pseudorandom number generator it has the advantage of reproducibility when the same seed is used. [name] will maintain the randomization list, password protected, on a remote drive maintained by the Department of Urology, and will provide the random assignment to the study coordinator as each patient is enrolled. Because surgery dates are scheduled weeks in advance, there is no concern about inability to access the randomization list. A biostatistician who works for [name] and is not otherwise connected to this trial will also have access to the random assignments and can provide them to the study coordinator in the unlikely event that [name] is unavailable. Only [name] and the biostatistician ([name]) have access to the remote drive.

b. Primary outcome variable.

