Additional subanalyses (both ITT and per protocol) will be performed with stratification by arm compliance (proportion of scheduled subcutaneous heparin doses administered), performance of pelvic lymphadenectomy (including number of nodes removed), performance of open or robotic surgery (including differences in operative time), and other demographic and comorbidity criteria (including history of VTE, cancer, and other risk factors included in the Caprini Score) to identify patients at highest risk for VTE. Surveillance bias will also be evaluated, as mentioned above, by the differential performance of diagnostic imaging.

e. Interim Analyses.

Two interim analyses of the primary endpoint are planned with potential early stopping for efficacy or futility. O'Brien-Fleming boundaries were used, as implemented in PASS v. 11 (NCSS Software, Inc., Kaysville, UT). The total sample size needed for 82% power with a 1-sided test is 666 (333 per treatment arm), based on 2000 simulations. The interim analyses will be conducted after 1/3 and 2/3 of patients are enrolled (222 and 444, respectively). Alpha-spending at the 2 interim analyses and final analysis is .001,

.015, and .033 (cumulative alpha spent .001, .015, .048), respectively. The futility boundaries at the 1st and 2nd interim analyses, and final analysis are $p=0.816$, 0.272 , and 0.070 , respectively.

At each interim analysis the rates of the 3 safety endpoints (lymphocele, major bleeding, and hematoma) will also be evaluated and 95% confidence intervals calculated. Unacceptable rates for these endpoints are $\geq 15\%$, $\geq 5\%$, and $\geq 10\%$, respectively. If lower 95% confidence bounds meet or exceed these unacceptable rates the trial will be halted for further review and consideration of early stopping.

8. Risks

- a. Medical risks, listing all procedures, their major and minor risks and expected frequency.

Administration of subcutaneous heparin:

1. Major risks:

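### Section 7d commits to no lymphadenectomy-adjusted comparison of symptomatic lymphocele, so this primary safety test gives up some power and can mislead when the arms differ by chance

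*Combined protocol and SAP*

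**What the plan says.** - **Section 7a** stratifies the randomisation by two factors: "with stratification for type of surgery (robotic/laparoscopic vs. open) and subcohort membership".
- **Section 3 (Background)** names lymphadenectomy alongside open approach as a VTE risk factor: "several-fold greater risk for undergoing concurrent lymphadenectomy or open surgical approach". On lymphocele it cites an early 38-patient report of an "increased rate of lymphoceles associated with subcutaneous heparin after RRP with pelvic lymphadenectomy". It also cites a later report of 579 patients having pelvic lymphadenectomy, which "showed no statistically significant difference in lymphocele rate by screening pelvic ultrasound".
- **Section 7b** makes symptomatic lymphocele one of three primary safety outcomes and puts its rate at around 10% or less.
- **Section 7d**, on checking balance: "Comparisons will include factors such as age, race, BMI, comorbidities, prostate volume, tumor stage, operative time, and blood loss". On adjustment: "Logistic regression will be used if adjustment is required for any potential confounders not balanced by randomization". On safety: "Similar comparison of univariate rates, and adjusted odds ratios will be used for the 3 primary safety endpoints". No covariate is named for any of these models.
- **Section 7d, additional subanalyses**, lists "performance of pelvic lymphadenectomy (including number of nodes removed" as one of several stratifying factors. The stated purpose is to find the patients at highest VTE risk.

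**The concern.** Both heparin and lymphocele reports discussed in the Background concern patients who had pelvic lymphadenectomy. If lymphoceles arise mainly in those patients, the crude comparison in 7d pools men at risk with men at little risk. This has two consequences. The test loses some power to detect the harm that the protocol says makes urologists wary. And in a given trial, a chance difference between arms in the share having lymphadenectomy moves the crude lymphocele difference up or down, so a real harm can be partly hidden.

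The provisions in 7d do not settle this. The adjusted odds ratios have no named covariates and the adjustment rule waits for an observed imbalance, so the model is chosen after the data are seen. The subanalyses split the data by lymphadenectomy but promise no combined, lymphadenectomy-adjusted comparison of the arms, and they are directed at VTE.

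**Working it through.** **1. The plan's own figure.** Inputs from 7d and 7e: VTE 5% against 1.5%, one-sided 0.05, 333 per arm. Mean rate 0.0325.
- SE0 = sqrt(2 × 0.0325 × 0.9675 / 333) = 0.01374
- SE1 = sqrt((0.05 × 0.95 + 0.015 × 0.985) / 333) = 0.01368
- Power = Φ((0.035 − 1.645 × 0.01374) / 0.01368) = Φ(0.906) = 81.8%

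Simulation with the two interim looks and stated futility bounds gives 82.6%. The stated 666 and 82% reproduce. No power is stated for lymphocele.

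**2. Lymphocele, crude test.** Control rate 10% (the upper figure in 7b); heparin rate 17.5% (assumed, ratio 1.75); two-sided 0.05; 333 per arm.
- SE0 = sqrt(2 × 0.1375 × 0.8625 / 333) = 0.02669; SE1 = 0.02653
- Power = Φ((0.075 − 1.96 × 0.02669) / 0.02653) = 80%; simulation gives 81%

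**3. Lymphocele, stratified test.** Assume all lymphoceles occur in lymphadenectomy patients, with share q. The documents give no share, so q runs from 40% to 80%. Only the lymphadenectomy stratum (333q per arm) then carries information, with rates 10%/q and 17.5%/q. The same formula within that stratum gives:

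| Share q | n per arm in stratum | Rates in stratum | Stratified power | Crude power |
|---|---|---|---|---|
| 40% | 133 | 25.0% v 43.8% | 90% | 81% |
| 60% | 200 | 16.7% v 29.2% | 85% | 81% |
| 80% | 266 | 12.5% v 21.9% | 82% | 81% |

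Mantel-Haenszel simulation agrees. Type I error of both tests is about 5% at every share.

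**4. Alternative reading of the 10%.** Suppose 10% is the rate within lymphadenectomy patients, rising to 17.5% there. Overall rates are then 4% v 7%, 6% v 10.5% and 8% v 14%. Simulated crude against stratified power is 40% v 43%, 56% v 59% and 70% v 72%, a gain of about 1.5 to 3 points.

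**5. Chance imbalance.** The SD of the difference in share between arms is sqrt(2q(1 − q)/333): 3.8, 3.8 and 3.1 points. A difference of 5 points or more in either direction has probability about 19%, 19% and 11%.

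Take 5 points fewer in the heparin arm, under the assumptions of step 3. At q = 40% the expected crude difference is 0.375 × 43.75% − 0.425 × 25% = 5.8 points instead of 7.5; at 60% and 80% it is 6.4 and 6.6. Crude power falls to about 60%, 68% and 71%. Stratified power stays at about 90%, 85% and 82%.

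**6. False positives.** With no heparin effect and 8 points more lymphadenectomy in the heparin arm, the crude two-sided 5% test rejects in about 11%, 8% and 7% of trials. An excess that large in that direction occurs in only about 2%, 2% and 0.5% of trials.

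**7. VTE.** Assume lymphadenectomy multiplies VTE risk by 3 to 5 (the Background says several-fold). A 2-SD imbalance shifts the difference by 2 × SD × r × (RR − 1), where r = 5% / (1 − q + q × RR). At q = 40% and RR = 5: 2 × 3.8% × 1.92% × 4 = 0.6 points. At q = 80% and RR = 3: 2 × 3.1% × 1.92% × 2 = 0.2 points. The planned effect is 3.5 points.

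**The case against.** The best defence is that 7d already allows for this. The balance list is open-ended, the adjustment rule covers any confounder found unbalanced, adjusted odds ratios are promised for the safety endpoints, and lymphadenectomy is named in the subanalyses. A large imbalance would probably be caught: 8 points gives z = 8/3.8 = 2.1 or 8/3.1 = 2.6, p = 0.035 or 0.010. This stands as far as it goes. It would be wrong to infer that lymphadenectomy is absent from the plan. But permission is not commitment, and the rule is weakest where it is needed. A 5-point imbalance gives z = 1.3 to 1.6, which a balance test at 0.05 would pass, yet it costs the crude test 10 to 21 points of power under the assumptions of step 3. Nor does an imbalance rule recover efficiency when the arms are balanced.

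The second defence is that the gain depends on favourable inputs. A 40% share with a 10% overall rate implies 25% symptomatic lymphocele among control lymphadenectomy patients, which is high beside the 25-50% that 7b gives for screening-detected cases. No passage says that lymphocele is confined to these patients, and the 579-patient report found no significant heparin effect. This also stands, and it limits the size of the point.

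**Conclusion.** The point holds as a modest, nearly free improvement to the section 7d analysis of symptomatic lymphocele. The gain in power is about 1 to 9 points if 10% is the overall rate and all lymphoceles follow lymphadenectomy, and about 1.5 to 3 points if 10% is the rate among lymphadenectomy patients. The stronger argument is protection in the individual trial: an imbalance of 5 points or more has probability of roughly 11 to 19%, about half of it in the direction that masks harm.

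A reader might infer more than the documents support:
- **That the randomisation in 7a is defective.** Stratifying it while keeping the crude test would change power by at most about 2 points. The gap is in the analysis.
- **That chance imbalance makes the crude test invalid, or will pass for a heparin effect.** The overall false-positive rate stays near 5%. Marked inflation needs an imbalance seen in 2% of trials or fewer.
- **That the primary VTE result is at risk.** The shift there is about 0.2 to 0.6 points against a planned 3.5.

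All sizes rest on assumed shares and lymphocele rates, because the documents supply neither the share nor the rate among lymphadenectomy patients.

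**What to change.** In 7d, state that the symptomatic lymphocele comparison will be stratified by pelvic lymphadenectomy (a Mantel-Haenszel test or a logistic regression term) whatever the observed balance.

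Use planned lymphadenectomy, recorded before randomisation, if it is known by then; the documents do not say when it is decided. Otherwise use performed lymphadenectomy. Note that it follows the preoperative dose, but that section 4c keeps the urologist blinded to allocation and to that dose during surgery.

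The same term in the VTE model is optional. The randomisation strata, sample size and visits do not change. The cost is one field on the enrolment form and one sentence in 7d.
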